**Patient Reported Outcomes used for Weekly
Internet-based DEtection of progressive
disease in lung cancer;
a randomized controlled trial**

Study title	
ProWide
 
Patient Reported Outcomes used for Weekly Internet-based DEtection of progressive disease in lung cancer; a randomized controlled trial

Protocol committé	
[name] [name], PhD student, West Jutland Hospital, Herning, principal investigator
 
[name], DMsc., Senior Consultant, West Jutland Hospital, Herning
 
[name] [name], PhD, Senior Consultant, professor, University Hospital Aarhus and West Jutland Hospital, Herning
 
[name], PhD, Senior Consultant, Rigshospitalet
 
[name] [name], PhD, Senior Consultant, Associate professor, Rigshospitalet
 
[name], WestChronic, West Jutland Hospital, Herning
 
[name], clinical lecturer, MPM, Danish Lung Cancer Registry
 
[name] [name], Senior Consultant, University Hospital Odense
 
[name] [name], PhD, Research Group Head, Danish Cancer Society
 
[name] [name], Department of Oncology, Aarhus University Hospital
 
[name] [name], PhD, Senior Consultant, Associate professor, University Hospital Aarhus
 
[name], Health Economist, Senior Project Manager, Danish Cancer Society

Institutions	Oncology departments in Denmark
Population	Lung cancer patients who have finished induction treatment for lung cancer. Eligible are patients with stage III disease treated with palliative intent, and stage IV lung cancer, regardless of treatment intent. Maintenance treatment is allowed.
Background	According to the national Danish follow-up program for lung cancer, patients are followed with clinical controls and a contrast enhanced CT-scan of the thorax and upper abdomen, every 3 months the first 2-3 years, then every 6 months until 5 years ¹ . In a palliative follow-up, CT scans are performed every 3 months after ended induction treatment. In case of continuous maintenance treatment, CT scans

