We will conduct a randomized controlled trial (RCT), comparing the two arms with respect to overall survival, progression-free survival, performance status at relapse, quality of life during follow-up/ and type of treatment initiated at the time of progressive disease. Finally, the use of healthcare resources will be calculated and compared at the end of the study.

Methods

The study is divided into two consecutive phases.

1. **Defining the PRO application** for symptom monitoring is inspired by a literature review, the Danish national lung cancer clinical guidelines¹¹, analysis of historical PRO data and study group consensus. The questions have been adapted to a Danish setting with feasibility testing prior to trial initiation. The process includes the construction of an application for mobile phones, tablets and laptops with an algorithm for sending notifications to clinicians.
2. Testing the PRO-tool in a **randomized multicentre trial**. See below for details.

Defining the PRO application

Denis et al have validated and published a list of 12 core symptoms in lung cancer and developed an algorithm for a web application. Certain combinations of symptoms and symptom-scores will send a notification to the hospital. Denis et al. found that the combinations and severity of the above symptoms had a high sensitivity and specificity for detecting relapse¹²⁻¹⁴.

The details of the algorithm have however not been fully published, which is why the model could not be fully adapted to this study.

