The randomized clinical trial of adding weekly PRO

Design and setting

The main part of the study consists of a multicenter randomized trial in order to assess the effects of the weekly PRO intervention. The design follows the overall setup presented in the publication by Denis et al, however, adapted to a Danish setting, as described above, including the Danish guidelines for evaluating CT scan in both arms². The randomization and baseline data collection will be made in the IT system (AmbuFlex) by the oncologist at the time of enrollment.

Implementation of the intervention

The intervention is illustrated in Figure 1. *In the experimental arm*, patients will be asked to fill in the PRO questionnaire every week via an internet connection, and they will also be asked to fill in HRQoL questionnaires at any outpatient attendance. However, if their weekly reported symptoms result in a notification, the clinician will contact the patient, and after verification of symptoms, schedule a visit at the clinic for physical examination and evaluation. If relapse or progression of disease is suspected an extra CT scan will be made, otherwise the patient will continue response evaluation/follow-up according to the usual schedule. The clinicians are allowed to reschedule the CT scan based on the phone call alone.

Both the HRQoL measurements and the web application will be administered through a web page that is designed for use on mobile phones, tablets and laptops(AmbuFlex¹⁹). The data will automatically be transferred in real time to a computer server, where notifications are generated and sent to clinicians if the prespecified symptom thresholds are exceeded. Data is automatically scored and will be available in easily interpretable visual reports in the AmbuFlex system.

If participants do not fill in the web-based questionnaire at pre-specified times, a reminder will be sent using a text message to their mobile phone and a message will appear for the clinical staff at the daily notification list.

[figure not shown]

Figure 1. Flow-chart showing the PRO-intervention in the randomized clinical trial.

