The study plan for the randomized clinical trial is outlined in Table I. In the standard arm, all patients will be followed with CT-scan with the standard of care intervals and asked to fill in the web-based HRQoL questionnaires every 2 months. In the experimental arm, patients will additionally be asked to fill in the web-based PRO questionnaire on a weekly basis. If a detrimental change (See appendix) is noted in the patient's weekly responses to the PRO questionnaire, the patient will be contacted by a study nurse for verification of symptoms. If the symptoms are verified, the patient will be treated by the clinical staff according to standard procedures. If progressive disease is suspected, the patient will have the CT scan rescheduled to as soon as possible. All CT-scans will be described and evaluated by standard practice. It will entirely be up to the treating physician to interpret the results of the CT scans and to define the time of progression as well as the following treatment.

Evaluation at screening, prior to inclusion

The objective of these evaluations is to identify patients, who meet the specified Inclusion- and exclusion criteria. The patient will be informed verbally and in writing. Only patients who have signed informed consent will be included. Following examination and data will be collected prior to inclusion:

- Histological or cytological verification of lung cancer
- Disease stage at treatment start
- Prior treatment and/or maintenance treatment

- Baseline CT scan of the thorax and upper abdomen, showing no signs of progression, after completion of the first treatment for lung cancer, performed within 28 days of randomization.
- Baseline performance status (according to the ECOG's scale¹³), estimated within 14 days of randomization

The patient will be asked to fill in baseline health-related quality of life (EORTC QoL-30/LC13, HADS, EQ-5D-5L) questionnaires via E-Boks immediately after inclusion and then every 2 months.

Additional evaluation for the intervention arm, after inclusion

- Weekly response to the PRO application
- If detrimental changes in PRO responses, earlier evaluation, described above

CT evaluation according to standard follow-up/response evaluation, all participants

- CT-scan of the thorax and upper abdomen, to evaluate the time of progression (or relapse)

Evaluation at relapse or progression

- CT-scan of the thorax and upper abdomen
- Performance status
- Planned 2nd line treatment

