- Categorization of the performed CT scan as prescheduled as a result of a PRO notification

Study period:

Patients will be followed for two years after inclusion in case of non-progressive disease. In case of progressive disease or relapse, the patient will exit the study. For survival analysis and further evaluation, patients will be followed until death or up to 5 years from inclusion.

Endpoints:

The primary outcome measures that will be compared between the experimental and control arm is overall survival with an observation time of 24 months.

The secondary outcome measures are

- Performance status at the time of progressive disease
- Progression-free survival
- Health-related quality of life
- Cost-effectiveness and hospital resource use and costs
- Type of treatment at the time of progressive disease

Time to progression as well as performance status at progression compared to performance status at enrolment into the study may be used to investigate, whether the intervention leads to earlier detection of and better performance status at the time of progression. Quality of life differences may provide insights on possible other patient perceived benefits to the web-mediated follow-up.

Sub-studies

A parallel research project has been financed and will focus on benefit in terms of quality of life and better patient involvement through qualitative interviews with patients included in the study. With qualitative interviews, we aim to describe how participants experience the web-based PRO application and to explore the mechanisms of action related to PROs as a mean of patient involvement. Moreover, we aim at exploring how the intervention influences patients' fear of cancer recurrence and their psychosocial well-being. We will apply the method of an interpretive description as an inductive, flexible research strategy to generate knowledge relevant within a clinical context²². Individual semi-structured interviews will be conducted with 8-10 patients from each arm. After one year, follow-up interviews will be conducted with the same participants in order to explore transformations in the patients' experiences and give new insights in barriers and opportunities for patient involvement in follow up of lung cancer (For details, see appendix, sub-study 1).

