In the randomised study by Denis et al.² the difference in 1-year survival in control vs. PRO arm was 49% vs. 75% with the significant hazard ratio of 0.33 in their sample of 60 vs. 61 individuals in the two study arms. A power calculation based on a log-rank test for difference in survival with these anticipated survival rates and a follow-up time of 1-year results in for 53 patients in each arm. Given the remarkable difference between the two arms, a more conservative estimate has been calculated for a relative improvement of approximately half this size.

The crude overall 1-year survival in Denmark of 46.2%⁹, but given that patients included in the study are responders of initiated treatment and presumably have better survival, 50 % 1-year overall survival is assumed to be the survival rate in the control arm. A relative improvement of approximately half the size found by Denis et al.² would result in an anticipated survival rate of 63.2%. A difference of this size would require 221 individuals in each group (Alpha 5%, Beta-1 80%).

However, the feasibility study revealed a compliance ratio of 90%, which then requires a total number of 492 patients.

Power calculations were performed in STATA 14.2 using the procedure for two sample survival comparison with the log-rank test.

We aim to collaborate across hospitals to get as many participants as quickly as possible.

Statistics

The study will be conducted as a randomized phase III study. A temporary analysis will be made after 2 years of inclusion and determine whether the study holds enough promise to justify the continuation of patient enrollment. No predefined criteria for termination of the trial have been determined.

Cox proportional hazards regression will be used to estimate the hazard ratios for time to clinical deterioration, time or relapse, and the median time to deterioration.

OS will be compared between the control arms among all randomized subjects using a two-sided, log-rank test. Median OS will be estimated via the Kaplan-Meier method.

Health resources utilized are described in both arms. All hospital costs from the point in time from randomization to 1-year follow up are measured by DRGs (Diagnosis-related groups) and inflated to the price year 2018 using the Danish Hospital PL

(Price and Wage) index. CIs are estimated with bias-corrected non-parametric bootstrapping.

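### PRO-triggered CT scans exist only in the experimental arm, so recorded PFS is shorter there even with an identical disease course, and the plan gives no dating or interpretation rule

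*Combined protocol and SAP*

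**What the plan says.** The Aim section commits to "comparing the two arms with respect to overall survival, progression-free survival, performance status at relapse", and PFS is listed as a secondary outcome in the synopsis and under Endpoints.

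Scan timing is described by arm:

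- **Control arm** (Study plan): "In the standard arm, all patients will be followed with CT-scan with the standard of care intervals". The synopsis gives the off-treatment interval: "In a palliative follow-up, CT scans are performed every 3 months after ended induction treatment". During maintenance treatment the usual interval is 8, 9 or 12 weeks.
- **Experimental arm**: the same schedule plus alert-driven scans. Study plan: "If progressive disease is suspected, the patient will have the CT scan rescheduled to as soon as possible". Implementation of the intervention: "If relapse or progression of disease is suspected an extra CT scan will be made", and also "The clinicians are allowed to reschedule the CT scan based on the phone call alone".

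Study plan leaves the date of progression entirely to the treating physician. Under Evaluation at relapse or progression, one item is recorded about the scan: "Categorization of the performed CT scan as prescheduled as a result of a PRO notification".

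Endpoints says that time to progression may be used to study whether progression is detected earlier. Statistics says: "Cox proportional hazards regression will be used to estimate the hazard ratios for time to clinical deterioration, time or relapse". It does not mention PFS. I found no definition of the PFS event or its date, and no rule for unequal scan timing.

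**The concern.** CT-detected progression is dated when a scan shows it, not when it begins. If one arm has an additional route to an early scan, its dates move forward without any change in the disease. Finding progression sooner is what the intervention is for, so the better it works, the shorter recorded PFS becomes in its arm. A true gain in PFS would be partly masked for the same reason.

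At stake is the reading of PFS beside overall survival. An apparent PFS detriment, or a null result, could be taken as evidence on disease control when it reflects scan timing. The plan gives the analyst nothing to prevent that reading.

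**Working it through.** **1. The plan's own figure.** The documents give no figure for PFS. The overall survival sample size reproduces. One-year survival of 50% against 63.2% gives HR = ln(0.632)/ln(0.50) = 0.662. A two-proportion formula gives 221 per arm and the Freedman log-rank formula gives 219. With 90% compliance, 442/0.9 = 491.1, which rounds up to 492. This point does not touch that calculation.

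**2. Size by hand.** If onset falls evenly within a scan interval of length L, the mean wait for the scheduled scan is L/2. With an alert CT 2 weeks after onset (assumption), the mean wait is 2 − 2²/(2L) weeks, because the scheduled scan sometimes comes first. For L = 13 weeks (3 months) these are 6.5 and 1.85 weeks, a gain of 4.65 weeks. If half of progressions are found by alert, the average shift is 0.5 × 4.65 = 2.3 weeks, about half a month.

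**3. Simulation with no true effect.** There were 246 patients per arm, with the same progression and death process in both. PFS is the earlier of detected progression and death, censored at 24 months, and there were 400 trials per setting. From the documents: the arm size, the 24-month follow-up, and scan intervals in the stated range (2 and 3 months used). Assumed: median true time to progression of 4 or 6 months, the share of progressions found by alert CT, about 2 weeks from symptom to CT, and a median of 8 months from progression to death.

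Cells show the HR (experimental vs control) and, in brackets, the share of trials in which a two-sided 5% log-rank test shows worse PFS (nominal 2.5%). Monte Carlo error is at most about 2.5 points.

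| True median, CT interval | 25% alert, 0% control ad hoc | 50%, 0% | 75%, 0% | 50%, 25% |
|---|---|---|---|---|
| 4 mo, 2 mo | 1.03 (5%) | 1.06 (9%) | 1.09 (16%) | 1.03 (4%) |
| 4 mo, 3 mo | 1.04 (7%) | 1.10 (20%) | 1.16 (40%) | 1.05 (6%) |
| 6 mo, 2 mo | 1.03 (4%) | 1.05 (6%) | 1.06 (11%) | 1.02 (4%) |
| 6 mo, 3 mo | 1.04 (7%) | 1.07 (11%) | 1.12 (25%) | 1.04 (8%) |

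With no triggered scans in either arm the HR is 1.00. With 50% in both arms it is 0.99 to 1.01. In the second row at 50% alert, median PFS is 6.04 against 5.45 months, a difference of 0.59 months that agrees with step 2.

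**4. Sensitivity to the scan grid.** When all patients are scanned on nearly the same study days, many event times are tied and the HR depends on how ties are handled. In one setting (9-week scans, median 17 weeks, 50% alert) it was about 1.08 with Efron's method and 1.13 with Breslow's. With staggered scan dates and a 50% alert share, the HR is about 1.03 to 1.09 and false harm 4 to 15%. Adding 25% control ad hoc detection brings these to about 1.02 to 1.03 and 4 to 7%. Across all variants run with 25% control ad hoc detection, the HR lies between 1.00 and 1.07.

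**5. Testing repairs under the null.** Suppose 25% of control progressions are found ad hoc. Moving only the alert-detected progressions to the next scheduled CT then reverses the bias. With staggered dates the HR is 0.96 to 0.98 and false benefit 4 to 7%; on a synchronised grid they are 0.93 to 0.97 and 5 to 15%. Moving every unscheduled detection in both arms restores an HR of 1.00.

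**The case against.** A reader might infer that no control patient is ever scanned because of symptoms. The documents do not support that. Only the PRO trigger is confined to the experimental arm. The health economic appendix describes standard care as unsystematic symptom reporting and plans to cost telephone contact with control patients. The Introduction notes more frequent scanning during palliative treatment. The columns with 0% control detection are therefore an upper end, and the 20 to 40% false-harm rates among them are not expected values.

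Nor does the plan state that PFS will be analysed by Cox regression; that is an inference from the sentence on time to relapse. It nowhere reads shorter PFS as harm, so there is no outright contradiction between two stated interpretations.

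It is also fair that the authors partly anticipate the issue. They propose time to progression as a detection measure and record whether the scan at progression followed a notification. PFS is unpowered and carries no decision rule.

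All of this limits the size and tone of the point. It does not remove the point: the detection routes still differ by protocol, PFS is still compared, and recognising that a measure depends on detection is not a rule for dating or interpreting it.

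**Conclusion.** The point holds. Carried out as written, the PFS comparison is biased against the intervention unless ad hoc scans find control progressions at the same rate as alerts and ad hoc scans together do in the experimental arm. The direction follows from the design.

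The size is modest and conditional on the alert share, the delay from onset to CT, median PFS and the control ad hoc rate, none of which the documents give. The HR is about 1.03 to 1.16 with alert shares of 25 to 75% and no control ad hoc CT, and about 1.00 to 1.07 if 25% of control progressions are also found ad hoc.

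A reader might extend this to the primary result. That would be wrong, because the date of death does not depend on scan timing. The change should be made, but the trial's main conclusion does not hang on it.

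**What to change.** 1. Keep time to detected progression as the early-detection outcome. State that neither it nor PFS on actual detection dates is read as an effect on disease control.
2. Define PFS. Date every progression found at any unscheduled CT, in both arms and whatever the trigger, at the earlier of the next scheduled CT and death. Alternatively, use an interval-censored model with intervals bounded by scheduled scans, because a scan prompted by symptoms is not timed independently of progression.
3. Extend the CT categorisation at progression to scheduled versus unscheduled in both arms, and record each patient's planned scan interval. The interval-censored option also needs the dates of negative scans; Data collection and analysis lists only the number of scans.
4. Reconcile the two descriptions of the alert scan. Implementation of the intervention has it added to the schedule, whereas Study plan has an existing scan moved. The later scan grid, and hence the next scheduled CT, depends on which is meant.

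The cost is SAP wording, a few extra data fields and somewhat coarser progression dates. No change to sample size follows.

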	
are performed at prespecified intervals, usually every 8th, 9th or 12th week depending on treatment type.
 
Recently, a study by Denis et al.² suggested, that weekly patient-reported (PRO) symptoms monitoring during maintenance therapy or follow-up of lung cancer patients, could help to early identify patients with relapse or progression of disease. In their randomized phase III trial, conducted in France, they found a median survival of 19.0 months (12.5- non-calculable) for the PRO intervention group vs 12.0 months (8.6-16.4) in the control arm (p=.001). HR=0.325(0.157-0.673).
 
One-year survival was 74.9% (56.6-86.4) vs 48.5% (31.9-63.2) (p=.05) with a benefit of 26 %.
 
A significant benefit in both quality of life and survival has also been shown in another phase III study by Basch et al that tested weekly PRO monitoring of patients undergoing treatment for metastatic cancer, of whom approximately 25% had lung cancer^{3,4}. The median overall survival was 31.2 months (24.5-39.6) in the PRO group and 26.0 months (22.0-30.9) in the standard of care group, HR=0.83 (0.70-0.99).
 
One-year survival was 75.1% (70.7-79.0) vs 68.6% (63.2-73.6) (p=.05), showing a survival benefit of 6.5 %.
 
Inspired by these encouraging results, we propose to test, in a Danish setting, whether adding weekly monitoring of patient-reported symptoms, can improve survival by early detection of progressive disease in lung cancer patients. The weekly monitoring will be added to the standard CT evaluation scans with clinical control and contrast-enhanced CT of thorax and abdomen.

Endpoints	
Primary endpoint:
 
 • Overall Survival 
Secondary endpoints:
 
 • Performance status at the time of progressive disease • Progression-free survival • Quality of life • Cost-effectiveness and hospital resource use and costs • Type of treatment at the time of progressive disease

Evaluation criteria	
All patients will have a baseline CT-scan of the thorax and upper abdomen performed prior to treatment and an evaluation CT scan at the time of enrolment. CT scan will be repeated for assessing signs of relapse or progression due to standard follow-up/response evaluation procedures.
 
Health-Related Quality of life (HRQoL) will be measured using EORTC QOL-C30⁵/ LC13⁶, EQ-5D-5L⁷ and HADS⁸ every 2 months during the study period.

Methodology	Multicentre phase III trial

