Eligible are patients with stage III lung cancer where the treatment intention is palliative and stage IV lung cancer regardless of treatment intent, who have received first-line induction treatment and have stable disease or better response after induction therapy. Maintenance treatment of any kind is allowed during the study period. Patients will be stratified by centre, stage and by main histology; small-cell lung cancer vs. non-small cell lung cancer.

Inclusion Criteria

1. Patients with lung cancer (NSCLC or SCLC) with stage III treated with palliative intention, or stage IV, regardless of treatment intention.
2. 1st line induction treatment* started/completed prior to the current evaluating scan
3. Non-progressive** disease at first CT scan evaluating 1st line induction treatment

4. Diagnosis proved by cytology or histology
5. Age \geq 18 years
6. Performance status (PS) \leq 2
7. First evaluation CT scan performed within four weeks from enrolment
8. The patient has given his/her written informed consent before any specific procedure from protocol

** Induction treatment includes:*

- *Standard doublet chemotherapy*
- *Immunotherapy*
- *Targeted therapy*
- *Palliative radiotherapy*
- *Local treatment of oligometastatic disease, including surgery and stereotactic radiotherapy*
- *Any combination of the above-mentioned treatment modalities. Patients are eligible regardless of whether they at the time of inclusion continue maintenance treatment or not*

*** Patients with stable disease or better response, defined by the treating clinician, are eligible. Patients receiving immunotherapy are eligible if pseudoprogression is suspected based on clinical response and treatment is continued. Patients receiving 1st line "treatment beyond progression" are eligible*

Exclusion Criteria

1. No internet access
2. No E-boks access
3. No mobile phone
4. Persons deprived of liberty or under guardianship or curators
5. Dementia, mental alteration or psychiatric disease that can compromise informed consent from the patient and/or adherence to the protocol and the monitoring of the trial
6. Pregnant or breastfeeding women
7. Patient participating in another interventional study during the surveillance period. This is only relevant for studies that might interfere with the intervention. Participation in protocols related only to treatment will not preclude participation in the present study. Cases of doubt will be settled by the protocol committee.

Time of enrolment

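### The date of progression is left to a treating physician who knows the arm, so PFS dates for the same scans can differ between physicians and could differ by arm

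*Combined protocol and SAP*

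**What the plan says.** The Study plan section covers both the reading of the scans and the dating of progression. On reading: "All CT-scans will be described and evaluated by standard practice". On dating: "It will entirely be up to the treating physician to interpret the results of the CT scans and to define the time of progression". The documents name no response criteria, independent or blinded reading, or confirmation rule. They do not say whether the date is that of the scan, a later scan or the clinic decision.

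Progression-free survival is a secondary endpoint in the synopsis and in the Endpoints section, without a definition. The Statistics section offers a Cox model for times to deterioration and relapse, but gives no event, origin, dating or censoring rule. The Endpoints section adds that time to progression may be used to judge whether the intervention detects progression earlier.

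Blinding is not mentioned, but knowledge of the arm follows from the design. Under Design and setting: "The randomization and baseline data collection will be made in the IT system (AmbuFlex) by the oncologist at the time of enrollment". Under Implementation of the intervention, notifications go to clinicians, and: "The clinicians are allowed to reschedule the CT scan based on the phone call alone". The data collected at progression include whether a PRO notification led to the scan.

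The synopsis Background gives the scan intervals. On maintenance, CTs "are performed at prespecified intervals, usually every 8th, 9th or 12th week depending on treatment type". In palliative follow-up off treatment, "CT scans are performed every 3 months after ended induction treatment".

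The Inclusion Criteria footnote leaves room for equivocal growth at entry: "Patients receiving immunotherapy are eligible if pseudoprogression is suspected based on clinical response and treatment is continued". It also admits patients on first-line treatment beyond progression.

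**The concern.** Leaving the diagnosis of progression to the treating physician is a reasonable pragmatic choice. Leaving the date to the same person, with no rule, is a separate choice and an avoidable one. For the same series of scans, one physician may take the first CT that showed growth, another the next CT that made it unequivocal, and a third the visit at which treatment was changed. All three comply with the plan.

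Variation between physicians adds noise to PFS. If the habit also differs by arm, which is possible because the physician knows the arm and the reason for the scan, it adds bias. PFS and time to progression are compared between arms, and the latter is meant to show whether the intervention works through earlier detection. A date set by discretion weakens the quantity intended to test that mechanism.

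**Working it through.** **1. The plan's own calculation.** The only design calculation concerns overall survival. HR = ln(0.632)/ln(0.50) = 0.662. Freedman's formula gives 190 events at two-sided 5% and 80% power. The mean event probability is 1 - (0.50 + 0.632)/2 = 0.434, so 190/0.434/2 = 219 per arm, close to the stated 221. Then 221/0.90 = 245.6, rounded up to 246 per arm and 492 in total. No term depends on the date of progression, and the plan states no PFS figure.

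**2. Gap for one patient.** If one physician dates to a first equivocal CT and another to the next scheduled CT, the dates differ by one interval:
- on maintenance: 8, 9 or 12 weeks;
- off treatment: 3 months = 52/4 = 13 weeks.

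**3. Shift in mean PFS between arms.**

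Shift = (share of progressions equivocal at first) × (difference between arms in the proportion of those dated to the later CT) × (interval).

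Both shares are assumptions; the documents give neither.

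| Equivocal share | Arm difference | Interval | Shift |
|---|---|---|---|
| 0.10 | 0.25 | 8 weeks | 0.2 weeks |
| 0.30 | 0.25 | 12 weeks | 0.9 weeks |
| 0.10 | 1.00 | 8 weeks | 0.8 weeks |
| 0.30 | 1.00 | 12 weeks | 3.6 weeks |

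Off treatment, 0.30 × 13 weeks gives 1.0 week at a difference of 0.25 and 3.9 weeks at 1.00.

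**4. Effect on the hazard ratio (simulation).** Assumptions, none from the documents: exponential progression times with no true arm effect, median PFS 4, 6 or 9 months, scans every 8, 9, 12 or 13 weeks, a 104-week cut-off, and 10% or 20% of progressions deferred by one scan in one arm only. The HR is the log-rank O-E estimate with 20,000 per arm. Simulation error on the log HR is roughly √(4/40,000) = 0.01.

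| Deferred arm | 10% deferred | 20% deferred |
|---|---|---|
| Experimental | HR 0.93-1.00 | HR 0.87-0.98 |
| Control | HR 1.02-1.08 | HR 1.05-1.14 |

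With 246 per arm, median PFS 6 months, deferral in the experimental arm and 1,500 replicates, the rejection rate of a nominal 5% two-sided test was 5.6% (10% deferred) and 7.7% (20%) at 8-week scans, and 6.1% and 11.8% at 12-week scans. The standard error is about √(0.05 × 0.95/1,500) = 0.6 points, so the values at 10% deferral are barely distinguishable from 5%.

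The deferred fraction here is the product of the first two factors in step 3. At a 25-point difference that product is 0.025 to 0.075, below anything simulated. The simulated cases are therefore strong contrasts, not central estimates.

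**5. A separate source.** If 30% of experimental-arm progressions are found by a prompt PRO-triggered scan (assumption), with identical dating in both arms, the same simulation gives an HR of 1.05-1.18 against the intervention. A dating rule does not remove this.

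**The case against.** The strongest reply is that this is a pragmatic trial with overall survival as its primary endpoint, and that progression judged in routine care is what the intervention is meant to influence. The Study plan section also lists the CT as the means of evaluating the time of progression, which is a partial anchor to the scan. Both points stand. The anchor, however, does not say which CT counts when growth is seen on more than one.

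A reader might infer that the arms will be dated differently, for instance that an alert-prompted scan invites dating at that scan while a routine scan invites waiting. The documents do not support this. They show that dating can differ by arm, not that it will, and they give no direction.

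A reader might also take 8-12 weeks as the size of the problem. It is the gap for a single patient on maintenance, and only if the later CT falls exactly one scheduled interval after the first. The plan describes no confirming CT and lets a scan be brought forward when progression is suspected. The difference between scan date and clinic date cannot be sized from the documents at all. Nor does the eligibility footnote give a rate of equivocal scans on study, because it concerns the entry scan.

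**Conclusion.** The point holds as a gap in the definition of a secondary endpoint. The plan gives the date of progression, not only its diagnosis, to a physician who knows the arm, and no other text limits that discretion. The effect on mean PFS is 0.2-0.9 weeks at a 25-point difference between arms and at most 0.8-3.6 weeks at a complete difference, for 10-30% equivocal progressions on 8-12 week intervals. Both shares are assumptions, and the direction is unknown.

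It would be tempting to read this as a threat to the main result. It is not: overall survival and the 492 patients do not depend on the date of progression. It would also be wrong to expect a dating rule to make PFS unbiased, since earlier PRO-triggered scans remain a separate and partly intended source of difference. The change should be made because it is cheap and removes an avoidable part of the problem.

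**What to change.** Keep the physician's judgement on whether progression occurred and fix the analysis date in the SAP, before any comparison by arm:

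> The PFS event date is the date of the first CT performed after randomisation that described the progression accepted by the treating physician. Growth already present on the enrolment CT does not count as an event unless further progression is described on a post-randomisation CT. Without such a CT, use the date of clinical progression or death, whichever comes first. Performance status and treatment at progression remain those recorded when progression is determined.

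The restriction to post-randomisation CTs is needed. Patients may enter with suspected pseudoprogression or on treatment beyond progression, and their growth may first have been described on the enrolment CT. A rule dating to the first CT that ever showed it would give them zero or negative PFS.

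The cost is one date field and a short check of CT reports for each progressor, because the Data collection and analysis section commits only to recording the number of CTs. Two limits remain. The PFS date may precede the visit at which performance status is recorded, and the physician still decides whether progression is accepted. A re-reading of a sample of progression scans without knowledge of the arm would address the second and is optional. Patient care does not change.
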